## **Online Diabetes Education Project: Virtual Diabetes Self-Management Education and Support Intervention IRB Protocol**

### **1.0 PHASE II RESEARCH PLAN (Pilot Randomized Control Trial, 3 months)**

During Phase II we will be conducting a 3 month pilot randomized controlled trial (RCT) of Virtual Diabetes-Self Management Education and Support (DSME/S), the treatment adapted in Phase I, to evaluate participant recruitment and retention rates, treatment and intervention satisfaction and estimate intervention effect sizes on our primary outcome of glycemic control (HbA1c) as well as on secondary outcomes such as diabetes-related distress, self-management behaviors and diabetes social support at baseline and treatment termination. Data will be collected at baseline and three months (treatment termination) at a federally qualified health center, telephonically, or virtually. Participants will be randomized to the virtual empowerment-based DSMES or a control group. All virtual DSME intervention group sessions will be held on an online platform, Zoom Med. The baseline assessment and intervention period will consist of 14 weeks. In the first 2 weeks participants will complete baseline questionnaires, interviews, and physiologic testing at a federally qualified health center, telephonically, or virtually. In weeks 3 to 10, participants will be simultaneously enrolled in 8 weekly virtual DSME classes. In weeks 13 and 14 of the intervention, participants will complete the post-treatment assessment battery (See Table 1). Patients who do not complete the intervention phase will also be invited to participate in the treatment termination assessment. The physiologic testing part of the assessment will be held at Detroit Community Health Connection, Inc. (DCHC) and other community-based locations TBD, based on participant feedback, telephonically, or virtually. DCHC is a non-profit community-based primary care organization that provides medical and dental services to the insured, uninsured and underinsured at six federally qualified health centers in the city of Detroit. Data analyses and dissemination of study findings are anticipated to be completed in months 11-12 of the study funding period. In Phase III of this project, we will be conducting qualitative interviews to better understand the acceptability and sustainability of the intervention as routine practice in a community-based clinic.

**Table 1. Detailed timeline of Phase I and Phase II**

TIMELINE	Q1			Q2			Q3			Q4		
	Dec 20	Jan 21	Feb 21	Mar 21	Apr 21	Jun 21	Jul 21	Aug 21	Sep 21	Oct 21	Nov 21	Dec 21
Study Activities												
Phase I												
Focus Group Recruitment	■											
Hire & Train Research Staff	■											
Conduct Focus Groups		■										
Analyze Focus Group Data		■	■									
Adapt Intervention Materials			■	■	■							
Intervention Recruitment		■	■	■	■	■						
Phase II RCT												
Randomization			■	■	■	■						
T0 Baseline Assessment							■					
T1 Post-Intervention Assessment								■				
Phase III Data Analysis												
Interviews and Focus Groups (participants and practitioners)										■	■	
Analyze and disseminate data										■	■	

## **2.0 BACKGROUND**

Diabetes is the 6th leading cause of death in Southeast Michigan.(15,16) One-third of people living in this area over the age of 50 have diabetes or pre-diabetes.(15,16) Michigan's age-adjusted diabetes death rates in 2009 were 26.6 for White males, 19.1 for non-Hispanic White females, 44.7 for Black males, and 33.6 for Black females (deaths per 100,000 population).(15,16) Diabetes is highly prevalent in Black men and women and they are more likely to be diagnosed with diabetes compared to non-Hispanic Whites.(17) In addition, they are disproportionately more likely to have uncontrolled blood glucose levels than their non-Hispanic White counterparts.(17)

Diabetes self-management education and support (DSME/S) is a cornerstone of successful diabetes management. Various methods have been used to reach the increasing numbers of patients with diabetes, including Internet-based education. A 2015 review found that DSME/S delivered via the Internet is effective at improving measures of glycemic control and diabetes knowledge compared with usual care. In addition, results demonstrate that improved eating habits and increased attendance at clinic appointments occur after the online DSME/S, although engagement and usage of Internet materials wane over time. Interventions that include an element of interaction with healthcare providers were seen as attractive to participants. Internet-delivered diabetes education has the added benefit of easier access for many individuals, and patients can self-pace themselves through materials. More research on the cost-benefits of Internet diabetes education and best methods to maintain patient engagement are needed, along with more studies assessing the long-term impact of Internet-delivered DSME/S.

Based on our previous work, the ***long-term goal*** of our research is to determine the most effective, practical, and sustainable approaches to provide virtual diabetes self-management education and support (DSME/S) to increase accessibility to DSME/S in clinical and non-clinical settings. The ***objective*** of this proposal is to examine the relative effectiveness, feasibility and acceptability of virtual DSME compared to a control group. To accomplish this objective, we will engage in a developmental phase and a validation phase [pilot randomized controlled trial (RCT)]. The RCT will be conducted with N=60 Black adult residents of Detroit, MI. Participants will be randomized to an enhanced usual care group or to the tailored virtual DSME/S. We ***hypothesize*** that 1) participants in the virtual diabetes approach will have improved outcomes over the control group, and 2) an evaluation of measures will confirm efficacy of the intervention. Measures will be collected at baseline and 3-months. The primary outcome will be change in A1c, depression, and self-management behaviors at baseline and post-intervention. Secondary outcomes include changes in weight, blood pressure, quality of life, and diabetes related distress. We ***hypothesize*** that 1) participants in virtual DSME/S approaches will have improved outcomes over the control group, and that 2) participants in the empowerment-based virtual DSME/S will achieve DSME/S skills at significantly higher levels than participants in the control group.

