**Specific Aim 3: Assess the impact intervention strategies developed in Aim 1 by:**

- conducting a pilot study of our DSME/S to evaluate participant recruitment and retention rates, treatment and intervention satisfaction and estimate intervention effect sizes on our primary outcome of glycemic control (HbA1c) as well as on secondary outcomes such as self-management behaviors, depression and diabetes social support at baseline and 3 months. Data from the pilot trial will help refine recruitment strategies, training materials, and protocol to be used in a larger clinical trial.
- conducting qualitative interviews to better understand the acceptability and sustainability of the intervention as routine practice in a community-based clinic.

**Overall Impact:** Data from the pilot RCT will help refine recruitment strategies, training materials, and the study protocol to be used in a larger cluster RCT. Our study will also identify strategies to increase patient participation in intervention research and improve dropout rates. This goal is in line with the mission of NIDDK to disseminate science-based information on diabetes, to improve people's health and quality of life.

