## **7.0 MEASURES**

### **Primary Outcome Measures**

Metabolic Control will be measured via hemoglobin A1c (HbA1c). HbA1c will be collected using the DCA 2000 point-of-care testing instrument.

Depression will be measured using the PHQ-9 (score  $\geq 10$ ) and The BDI-II, a 21-item self-administered questionnaire used to assess symptoms of depression. Depression will be measured using the Beck Depression Inventory (BDI-II). BDI-II items have been designed to correspond with DSM-IVTR diagnostic criteria. The BDI-II has been shown to have excellent test-retest reliability and validity when used in general populations as well for use with diabetes samples.

Regimen adherence will be measured using the Perceived Diabetes Self-Management Scale, a self-report questionnaire used to measure a broad range of management behaviors, such as insulin management, dietary management, blood glucose monitoring, symptom response, and parent assistance/supervision.

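### The plan does not settle whether HbA1c is the only primary outcome or shares that status with depression and self-management

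*Combined protocol and SAP*

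**What the plan says.** The combined protocol and SAP gives the outcome hierarchy in several places.

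- **1.0 Phase II Research Plan:** the pilot estimates effects on the "primary outcome of glycemic control (HbA1c) as well as on secondary outcomes such as diabetes-related distress, self-management behaviors and diabetes social support". Depression is not named.
- **2.0 Background:** "The primary outcome will be change in A1c, depression, and self-management behaviors at baseline and post-intervention". The next sentence reads "Secondary outcomes include changes in weight, blood pressure, quality of life, and diabetes related distress", so depression and self-management are absent from the secondary list.
- **3.0 Aims, Specific Aim 3:** "primary outcome of glycemic control (HbA1c) as well as on secondary outcomes such as self-management behaviors, depression and diabetes social support".
- **7.0 Measures, first list:** under the heading "Primary Outcome Measures" come HbA1c, depression and regimen adherence, the last measured by the Perceived Diabetes Self-Management Scale. On depression it says "Depression will be measured using the PHQ-9", with a cutoff of 10, and also names the BDI-II.
- **7.0 Measures, Secondary Outcome Measures:** BMI, blood pressure, social support, distress and quality of life. Depression and self-management are not listed.
- **7.0 Measures, Specific Aim 2 analysis paragraph:** HbA1c is labelled primary and diabetes management secondary. Depression symptoms is a dependent variable with no tier.
- **7.0 Measures, Power Analysis:** HbA1c only.

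Section 2.0 also states the hypothesis that "an evaluation of measures will confirm efficacy of the intervention".

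**The concern.** A reader of section 2.0 and the first list in section 7.0 would expect three primary results. A reader of section 1.0, Specific Aim 3, the analysis paragraph and the power statement would expect one. Both readings have support in the current text, and nothing says whether one, any or all of the outcomes must be met.

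The choice could therefore be made once results are known. If HbA1c did not move but self-management did, the document could be cited for calling self-management a primary result. Section 5.0 says participants know their arm, and two of the three candidates are self-reported, so those two are the more exposed to expectation effects. Depression has a further open choice, because two scales are named and neither is identified as giving the outcome score.

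The stated purpose is to estimate effect sizes for a larger trial, so the main exposure is in how results are reported. The wording in section 2.0 about confirming efficacy makes that exposure larger than it need be.

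**Working it through.** **1. The labels side by side**

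| Place | HbA1c | Self-management | Depression |
|---|---|---|---|
| 1.0 Research Plan | primary | secondary | not named |
| 2.0 Background | primary | primary | primary |
| 3.0 Specific Aim 3 | primary | secondary | secondary |
| 7.0 Primary Outcome Measures | primary | primary (as regimen adherence) | primary (two scales) |
| 7.0 Secondary Outcome Measures | not listed | not listed | not listed |
| 7.0 Specific Aim 2 analysis | primary | secondary (as diabetes management) | no tier |
| 7.0 Power Analysis | powered | not powered | not powered |

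Self-management is the clearest conflict: primary in two places, secondary in three. Depression is primary in two and explicitly secondary in one. Section 7.0 points both ways: its secondary list agrees with three primaries, while its analysis paragraph does not.

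**2. What three primaries would mean for false positives**

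The plan gives no alpha for any outcome test; its only threshold is p < .10 for retaining covariates. Assume two-sided 0.05 per test and that any one success counts.

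- Independent outcomes: 1 − 0.95³ = 0.143.
- Equal pairwise correlation r, by integrating over one shared normal factor: 0.136 at r = 0.3, 0.125 at 0.5 and 0.109 at 0.7.

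The range is about 11% to 14%. There is no inflation if HbA1c alone is primary or if all three must be met.

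**3. The plan's power figure**

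Inputs from Power Analysis: 20% attrition, so 60 × 0.8 = 48, which reproduces; difference 0.6 SD; correlation 0.25; power 0.8 for a difference between average values of HbA1c. Assumptions: 24 completers per arm (two groups of about 12 in the treatment arm, the rest in control), two-sided 0.05, and no allowance for clustering within class groups.

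Power = Φ(0.6/SE − 1.96), with SE = √(v × 2/24). The detectable difference at power 0.80 is 2.802 × SE.

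| Contrast | v | SE | Power | Detectable at 0.80 |
|---|---|---|---|---|
| Mean of two measurements, baseline included | (1 + 0.25)/2 = 0.625 | 0.228 | 0.75 | 0.64 SD |
| Mean of three measurements | (1 + 2 × 0.25)/3 = 0.5 | 0.204 | 0.84 | 0.57 SD |
| 3-month value adjusted for baseline | 1 − 0.25² = 0.9375 | 0.280 | 0.57 | 0.78 SD |
| Unadjusted change (group by time, two assessments) | 2(1 − 0.25) = 1.5 | 0.354 | 0.40 | 0.99 SD |

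The stated 0.80 lies between the first two rows, so it is close to what a difference in average values gives. It does not carry over to a 3-month effect. The three-measurement row would match the three time levels in the analysis paragraph, but sections 1.0 and 2.0 schedule only baseline and 3 months.

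**The case against.** The strongest defence is that this is a pilot, that HbA1c is primary in every version, and that the analysis paragraph and the power statement both centre on it. On that view the matter is editorial. Much of this stands: it limits the consequence to reporting and interpretation. It does not remove the conflict, because Specific Aim 3 calls depression secondary and section 2.0 calls it primary, and neither can be read as shorthand for the other.

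Four stronger readings are tempting and should not be drawn.

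- **The type I error is inflated to 14%.** No section says that any one of three outcomes suffices, and no outcome alpha is given. The figure is conditional.
- **The stated power of 0.80 is simply wrong.** The plan refers to average values, for which 0.75 or 0.84 is obtained. The fair criticism is that this is a different contrast from a 3-month effect. The 24 per arm and two-sided 0.05 behind these figures are assumptions.
- **Section 2.0 promises significance on all three outcomes.** The words "will achieve DSME/S skills at significantly higher levels than participants in the control group" concern DSME/S skills only and do not reach HbA1c or depression.
- **The analysis section is wholly on the side of HbA1c alone.** The secondary list in the same section 7.0 omits both disputed outcomes.

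On the two scales, it can be said that the BDI-II is described as assessing symptoms and is named twice, while the PHQ-9 carries a cutoff, so the model's depression symptoms variable is plausibly the BDI-II. That is reasonable but not stated. Finally, baseline adjustment does not follow from the inconsistent labels. It is a recommendation, made because a single primary outcome still needs a single defined estimate.

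**Conclusion.** The point holds and should be fixed before analysis. The current text supports one primary outcome or three, depending on the section, with no rule to choose between them. This conclusion rests on the wording alone and needs none of the calculations.

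The size is modest. A false-positive risk of about 11% to 14% arises only under an any-one-counts rule with two-sided 0.05 per test, neither of which is in the plan. Once HbA1c is the sole primary outcome and the estimate is the baseline-adjusted 3-month difference, power at 0.6 SD and correlation 0.25 is about 0.57, assuming 24 completers per arm, two-sided 0.05 and no clustering.

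**What to change.** - **2.0 Background and 7.0 Primary Outcome Measures:** make HbA1c the only primary outcome, removing depression and self-management.
- **Secondary lists in 2.0 and 7.0:** add both outcomes. Name one depression score (BDI-II or PHQ-9) as the secondary outcome and the other as supportive. Report secondary outcomes as estimates with 95% confidence intervals.
- **2.0 hypotheses:** reword the claim about confirming efficacy to suit a pilot that estimates effects.
- **7.0 Specific Aim 2 analysis:** define the primary estimate as the between-group difference in 3-month HbA1c adjusted for baseline, at a stated two-sided 0.05, with time at the two scheduled assessments instead of three levels.
- **7.0 Power Analysis:** restate power for that estimate, with the completers per arm and alpha written out: about 0.57 at 0.6 SD, or about 0.78 SD detectable with power 0.80.

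The cost is wording in these places, with no added participants or visits. The trial gives up any primary claim on depression or self-management and carries a less favourable stated power.

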### **3.0 AIMS**

**Aim 1 (Phase I HUM00170437): Identify barriers and facilitators to mental health care utilization, diabetes self-management, and internet/computer accessibility and acceptability by:**

- Conducting 15 interviews with African American women and 15 interviews with African American men with diabetes
- Conducting semi-structured stakeholder interviews including mental health care providers at a Detroit-based health clinic.

**Specific Aim 2: Develop a virtual empowerment-based Diabetes Self-Management Education and Support (DSME/S) intervention to work in a community-based clinic based on what we learn in Aim 1. Development, adaptation and refinement will involve:**

- Developing an empowerment-based DSME/S based on our interviews and previous research.

**Specific Aim 3: Assess the impact intervention strategies developed in Aim 1 by:**

- conducting a pilot study of our DSME/S to evaluate participant recruitment and retention rates, treatment and intervention satisfaction and estimate intervention effect sizes on our primary outcome of glycemic control (HbA1c) as well as on secondary outcomes such as self-management behaviors, depression and diabetes social support at baseline and 3 months. Data from the pilot trial will help refine recruitment strategies, training materials, and protocol to be used in a larger clinical trial.
- conducting qualitative interviews to better understand the acceptability and sustainability of the intervention as routine practice in a community-based clinic.

**Overall Impact:** Data from the pilot RCT will help refine recruitment strategies, training materials, and the study protocol to be used in a larger cluster RCT. Our study will also identify strategies to increase patient participation in intervention research and improve dropout rates. This goal is in line with the mission of NIDDK to disseminate science-based information on diabetes, to improve people's health and quality of life.

## **4.0 PARTICIPANTS AND RECRUITMENT**

*Participants will be 60 Black men and women that are 18 years or older and meet the inclusion criteria listed below. During the Phase II pilot we will individually randomize each participant with a 50/50 randomization scheme to either virtual empowerment based DSME/S or a control group.*

**Inclusion:** Inclusion criteria for the Phase II (intervention) will include participants with all of the following identities: age 18 or older, Black, a diagnosis of T2D for six months duration or longer, ambulatory status, and currently under a physician's care.

Eligibility will be determined using a telephone screening (administered by a research assistant or project coordinator). Respondents who meet eligibility criteria will be invited to participate in the baseline screening assessment.

**Exclusion** For Phase II (intervention) we considered restricting eligibility to a higher-risk population of participants with A1c  $\geq$  8%. Preliminary data suggest that over 50% of the proposed study sample will have an A1c  $\geq$  8%. Focusing on all Black/African American men and women with type 2 diabetes allows us to cast a wide net for secondary prevention and public health impact. Persons who meet eligibility criteria will be invited to participate in the baseline screening assessment. While we have chosen the above eligibility criteria based on previous work, we will make adjustments to the future, larger trial, based on results and feedback from our proposed pilot.

**Recruitment** We plan to utilize the following strategies to enhance and maintain participation in the proposed study: Patients currently at the DCHC clinic and eligible for the study will be identified via electronic medical record (EMR) by DCHC facility

staff and provide the UM study team with names, phone numbers, and emails of eligible patients. The UM study team will then contact the potential subjects via email and by phone. The UM study team will not have access to patient EMRs. Flyers describing the study will be posted at each of the 6 DCHC clinics and in community-based locations. Interested participants will call the UM study team's central office phone number where they will be scheduled for screening. We also plan to recruit from the Michigan Center for Urban African American Aging Research Participant Resource Pool (MCUAAAR PRP). Flyers describing the study will be posted at the MCUARP center, including the central phone number for participants to reach the research staff. The research staff will be given a list of eligible male and female candidates from the research pool who have a Type 2 diabetes diagnosis; and a self-identified Black/African American identity from the MCUAAAR PRP will be invited to participate in the intervention. The MCUAAAR PRP is a research volunteer registry can be accessed by scholars conducting research of Black males, 55 years of age and older who meet their study criteria. [name] has previously conducted studies using older Black males with T2D recruited from the PRP. There are currently a total of 1424 active PRP members and 60.1% of male PRP members have T2D.

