**Randomization** Participants will be randomized to the virtual empowerment based DSME/S or a control group using a 50/50 randomization scheme. Participants will be aware if they are in the intervention group or the control group.

**Intervention (virtual empowerment-based DSME/S n=30)** Participants randomized into the virtual empowerment-based DSME/S group will receive 10 hours of DSME/S delivered by a Certified Diabetes Care and Education Specialist (CDCES) over 8 weeks delivered via the Zoom for Health at U-M service may be used for Protected Health Information (PHI, regulated by HIPAA). To ensure treatment fidelity, three DSME/S sessions will be selected at random and recorded and rated for fidelity to the above content by our research team.

**Control Group (Control n=30)** Participants randomized to enhanced usual care will receive referrals to community mental health providers, pedometers, gym memberships to a community-based venue, and intervention patient manuals. Based on several years of experience in Detroit, providing all participants with referrals, pedometers, and educational materials minimizes ethical concerns regarding assignment of underserved populations to receive a no-treatment control.

**Follow-Ups** Follow up assessments for both the virtual empowerment-based DSME/S group and control group will occur at three months (post-treatment assessment). Participants will return to the DCHC for follow-up assessments, telephonically, or virtually and the same measurements and surveys will be completed. Participants will be compensated \$20 for completing each assessment. Data will be stored in REDCap, a secure, web-based application hosted at UM.

**Maintenance of Samples** Strategies will be used to encourage attendance of group sessions and to complete follow up interviews. Reminder emails, texts and/or calls

will be sent before each session to remind participants by the study team. In addition, the study team will collect participant contact information from baseline through the follow up phase. The study team will also ask participants to provide additional contact person(s) that the study team can contact if they cannot reach the participant.

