### **Secondary Outcome Measures**

BMI will be calculated using height and weight. Height will be measured using a stadiometer. Weight will be measured on a high quality, calibrated digital scale. BP will be measured using the auscultatory method.

Diabetes Social Support will be measured using the Diabetes Social Support Questionnaire. Diabetes-related Distress will be measured using Diabetes Distress Scale (SF-12) and lastly, a validated Diabetes Quality of Life will be used to measure quality of life. Participants will also complete questionnaires that assess socio-demographic, behavioral, psychosocial, and health services utilization and are

validated in diverse populations with diabetes.

**Specific Aim 1:** Qualitative analyses will be conducted during the development phase and on the post-intervention focus groups and interviews. First, we will develop codes utilizing a grounded theory approach and will start with the formulation of categories and definitions developed directly from the text. Content from transcripts will be coded for themes and patterns. Through this process a coding manual and definitions will be finalized. The refined manual will be used to guide ongoing coding and pairs of coders will read subsequent transcripts keeping codes that achieve 80% agreement on code application. Analyses will be conducted using Dedoose. This data will be used to conduct a final refinement of treatment content as needed.

**Specific Aim 2:** The proposed study includes a sample size of 60 Black men and women, 30 in the intervention arm and 30 in the control arm. We will assess the impact of the intervention on HbA1c (primary outcome) and diabetes management (secondary outcomes) using multilevel modeling, with intervention group as a between-subjects factor (2 levels) and time as a within subjects factor (3 levels). HbA1c, depression symptoms, diabetes self-management, and social support at baseline and 3 months will be used as the dependent variables. Independent variables include intervention group, time of assessment, and interaction between time and intervention group. Random effects will be allowed for the intercept (to allow differences in baseline measurements) and the slope (to allow differences in the trajectories of change). Covariates e.g. length of time since diabetes diagnosis, age will be tested as predictors of the outcome and retained if significant at  $p < .10$ .

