**Power Analysis:** Assuming 20% attrition, we expect a final sample size of 48, approximately 12 per group (with 2 groups in the treatment arm). If we assume correlations of 0.25 between successive measurements of HbA1c, then this sample size will yield power of 0.8 to detect a difference of 0.6 standard deviation between average values of HbA1c in treatment and control groups.

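### Randomisation is not stratified on A1c and the HbA1c model does not condition on baseline HbA1c, so a chance baseline gap between arms carries into the effect estimate

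*Combined protocol and SAP*

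**What the plan says.** **Eligibility (section 4.0, Exclusion).** The sponsor writes that "we considered restricting eligibility to a higher-risk population of participants with A1c" of 8% or more, then takes all Black adults with type 2 diabetes who meet the other criteria. It expects more than half to be at or above 8%: "Preliminary data suggest that over 50% of the proposed study sample will have an A1c" at that level. On what follows, it says "we will make adjustments to the future, larger trial, based on results and feedback from our proposed pilot". That sentence does not name A1c.

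**Allocation (section 5.0, Randomization).** "Participants will be randomized to the virtual empowerment based DSME/S or a control group using a 50/50 randomization scheme". Section 4.0 adds that randomisation is individual. Strata, blocks and minimisation are not mentioned in the text available.

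**Analysis (section 7.0, Specific Aim 2).** On numbers, the plan states: "The proposed study includes a sample size of 60 Black men and women, 30 in the intervention arm and 30 in the control arm". The multilevel model has group, time and their interaction. HbA1c at baseline and at 3 months is the dependent variable, with a random intercept and slope. The covariate list is open; it gives diabetes duration and age as examples and keeps a covariate only if p < .10. Baseline HbA1c is not named, and no effect by A1c level is planned.

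**Power Analysis (section 7.0).** "If we assume correlations of 0.25 between successive measurements of HbA1c", the plan claims power 0.8 for a 0.6 SD difference with 48 analysed after 20% attrition.

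**The concern.** HbA1c is the outcome on which the pilot is to estimate an effect size (sections 1.0 and 3.0), and entry is deliberately wide on that same variable. In a trial of 60, plain allocation can leave the arms visibly different in baseline A1c.

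A group-by-time contrast from two visits is in effect a difference in change. When the correlation between visits is low, the arm that starts higher tends to fall further through regression to the mean. A baseline gap then looks like benefit if the intervention arm starts higher, and hides benefit if it starts lower. A random intercept does not remove this, because the fixed group term still lets the arms differ freely at baseline. At stake is the precision and credibility of the effect size carried forward to the larger trial.

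**Working it through.** **Inputs.** From the documents: 60 randomised 30/30, 20% attrition, correlation ρ = 0.25, target 0.6 SD, more than 50% at A1c ≥ 8%. Assumed: two-sided α of 0.05 (none is stated with the power figure), attrition equal by arm (60 × 0.8 = 48, or 24 per arm), equal SD at both visits, normally distributed HbA1c, a share at ≥ 8% of 50% to 70%, and ρ = 0.7 as a contrast.

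**1. The plan's own figure.** For the mean of k visits, the variance is (1 + (k − 1)ρ)/k.
- k = 3: variance 0.50. Power 0.80 needs 46 analysed, against 48 stated; power at 48 is 0.82. The sample size therefore reproduces, but only with three visits.
- k = 2, the visits actually planned: variance 0.625, power 0.73.

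The 0.6 SD is stated for average HbA1c, so it serves below only as a yardstick.

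**2. Chance of an imbalance.** Draw 30 from 60 without replacement, with K people at ≥ 8%. A gap of 20 points is 6 people.

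| K of 60 | P(gap ≥ 20 points) |
|---|---|
| 30 | 0.196 |
| 33 | 0.119 |
| 36 | 0.187 |
| 42 | 0.158 |

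(With K odd the smallest qualifying gap is 7 people, hence the lower value at 33.)

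**3. Size of the shift.** Splitting a normal variable with 50% to 60% above the cut puts the two stratum means about 1.6 SD apart.
- Baseline gap: 0.20 × 1.6 = 0.32 SD.
- Shift in the difference in change: 0.32 × (1 − ρ). At ρ = 0.25 this is 0.24 SD, and 0.24/0.6 = 40% of the target. At ρ = 0.7 it is about 0.10 SD, or 16%.

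A second route uses mean HbA1c directly. The SE of the baseline difference is √(2/30) = 0.26 SD, so a gap of 0.3 SD or more has probability about 0.25. A 0.3 SD gap shifts the contrast by 0.3 × 0.75 = 0.225 SD.

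**4. Standard error, 24 completers per arm, ρ = 0.25.**
- Group by time as planned: variance 2(1 − ρ) = 1.5; SE = √(1.5 × 2/24) = 0.354 SD.
- Allocation stratified at 8%, same contrast: 1.5 splits into (1 − ρ)² = 0.5625 from baseline and 1 − ρ² = 0.9375 from the rest. Stratifying removes about (1.6/2)² = 0.64 of the baseline part: 0.5625 × 0.36 + 0.9375 = 1.14; SE = √(1.14 × 2/24) = 0.31 SD.
- Baseline HbA1c as covariate, no stratification: SE = √(0.9375 × 2/24) = 0.28 SD, and the expected shift from a baseline gap is about zero.

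The variance ratio is 1.5/0.9375 = 1.6, so the planned contrast needs 60% more completers for the same precision. For a 0.6 SD difference at 3 months, power is 0.38 with the change contrast and 0.56 with the covariate. At ρ = 0.7 the SEs are closer: √(0.6 × 2/24) = 0.22 against √(0.51 × 2/24) = 0.21.

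**5. Could the pilot estimate an effect by A1c?** Take 12 per arm per stratum, baseline-adjusted.
- 95% half-width per stratum: 1.96 × √(0.9375 × 2/12) = 0.77 SD.
- Interaction SE: √(0.9375 × (2/12 + 2/12)) = 0.56 SD. Power for a 0.6 SD interaction is 19%, or 31% on the most favourable variant (mean of three visits).
- Power of 80% would need about 328 analysed.

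**6. Is A1c known before allocation?** Section 5.0 puts physiologic testing in a baseline assessment that settles eligibility, before randomisation. Table 1, as it reads, shows randomisation in February to June and T0 in July. Sections 1.0 and 5.0 also allow baseline by telephone or virtually, without saying how the point-of-care device in section 7.0 is then used.

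**The case against.** The strongest reply is that unstratified randomisation is valid and that chance imbalance is already inside the standard error. Across repeated trials the planned contrast is unbiased. A 0.24 SD shift is 0.24/0.354, or about 0.7 of a standard error, and at least 80% of allocations avoid a gap that large. The size also rests on ρ = 0.25, a power-planning assumption that may be too low. All of this stands. What remains is that the extra variance is avoidable at almost no cost, and that ρ = 0.25 is the plan's own figure.

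A reader might infer more: that the missing stratum and subgroup estimate are why the pilot cannot settle whether the larger trial should require A1c ≥ 8%. The documents do not support this. Section 4.0 makes a general promise to adjust the larger trial; that it covers the A1c threshold is a fair inference but is not stated, and section 3.0 lists recruitment, retention, satisfaction and overall effect sizes as the pilot's purposes. In any case, sixty people could not settle the threshold even with strata and an interaction term (step 5).

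Nor do the documents show that benefit is confined to people at or above 8%, so a claim that the pooled effect is diluted would be hypothetical.

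**Conclusion.** The point holds as a matter of precision and of a shift conditional on the allocation actually drawn. It does not make the randomisation invalid, and damage to the trial is not shown. A gap of 20 points or more has probability about 0.12 to 0.20; a 20-point gap moves the estimated change by about 0.24 SD at ρ = 0.25, or about 0.10 SD at ρ = 0.7. These figures rest on 30 per arm, normal HbA1c, equal SDs and a share at ≥ 8% of 50% to 70%; the standard errors also assume 24 completers per arm.

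The analysis matters more than the allocation. Conditioning on baseline brings the SE from about 0.35 to 0.28 SD by itself, while stratified allocation with the planned contrast brings it only to about 0.31. Adjustment does not restore the claimed power of 0.8.

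**What to change.** **Section 7.0, Specific Aim 2 (main change).** Estimate the 3-month HbA1c difference with continuous baseline HbA1c as a covariate, kept in the model whatever its p-value. Equivalently, keep the repeated-measures model but constrain the arms to a common baseline mean. Adding an A1c stratum as a main effect only is not enough: with two visits and complete data it leaves the group-by-time estimate unchanged.

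**Section 5.0, Randomization.** Use permuted blocks stratified by baseline A1c (< 8% / ≥ 8%) where the value is available before allocation, and include the stratum in the analysis. First reconcile Table 1 and the telephone or virtual baselines with the order in section 5.0. Where A1c cannot be read in time, covariate adjustment still deals with the linear imbalance.

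**Optional.** Report the treatment difference by baseline A1c with 95% CIs (about ±0.8 SD per stratum), labelled exploratory and not sufficient by itself to set the larger trial's A1c criterion.

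**Cost.** A sentence or two in the analysis section, a two-stratum allocation list and one extra table. The real constraint is that A1c must be read before allocation, which the documents do not yet secure.
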